2.3 Number of subjects

We estimate a total of 16 to 20 subjects would be enrolled in this study.

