Pain is by far the most common, and limiting, adverse event associated with PDT. Pain most often occurs early during illumination. Standard methods to decrease pain include the use of fans and the use of non-contact cold air skin cooling device during treatment. Given the larger size, number, and involvement of lesions, pain is often significantly greater in the OTR population, especially in field cancerization areas such as the head and scalp [10, 31]. Several, well-studied, pain-relieving techniques are available to complement the delivery of PDT including use of cooling fans, intra lesional anesthetics, nerve blocks, transcutaneous electrical nerve stimulation, and modified irradiance treatment. In addition, if the cooling alone is not sufficient and pain is moderate to severe (VAS>6-7), very brief interruption in illumination can be done. Daylight PDT has also been reported to have little to no treatment related pain.

SORT are especially at risk of developing multiple, aggressive or metastatic SCC, with an associated high morbidity and mortality rate. Prevention studies have typically looked at the effect of PDT in patients who had already developed many skin cancers and who may have undergone transplantation years prior to intervention. The current protocol involves early prevention of SCC development with field therapy in high risk patients who have only recently been transplanted. The proposed intervention would be an essential benefit that could be implemented in the early overall management of these patients, and may contribute to an improved long term quality of life.

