16. STATISTICAL CONSIDERATIONS

Characteristics of study subjects will be summarized by appropriate abstract statistics, including frequency, proportion and 95% Clopper-Pearson confidence interval (CI) for the proportion for categorical variables, median, and range for continuous variables.

Evaluable subjects for safety outcome measures will be those who complete any study visits or those who discontinue the study treatments due to adverse events (AE).
Evaluable subjects for efficacy outcome measures will be those who complete all study visits. At least 15-16 evaluable subjects for each of these analyses are expected.

Primary efficacy outcome measure will be the difference in the total number of AK/NMSC in the treatment areas compared to the control areas. All unique AK/NMSC

observed during the 3 year study period will be identified and summed in each area. The statistical significance of the difference will be tested using the Wilcoxon Signed-Rank Test.

Secondary safety and efficacy measure: Time to the occurrence of the first AK/NMSC in the control versus treated areas will be estimated using the Kaplan-Meier estimate. Changes in the p53 staining from baseline to end of treatment will be evaluated using McNemar's Test. Mean pain scores (VAS) and photo damage scale global scores of the study population will be compared with each respectively using Wilcoxon Signed-Rank Test.

Sample Size Determination: Safety will be evaluated using a one-sided confidence interval (as the lower bound is not of interest). At least fourteen patients will be evaluable for safety. If none of the patients have an adverse primary safety outcome, the upper bound of a 95% one-sided confidence interval is < 20%.

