17. ANALYSIS

17.1 Safety Analysis

The primary safety outcome measures will be estimated with 95% Clopper-Pearson CI: The proportion of evaluable study participants who had a grade 3 or higher AE or any serious adverse event that's determined to be at least possibly or probably related to study treatment, or any AE which is at least possibly or probably related to study treatment that causes permanent study discontinuation. AE's will be documented and kept in the study regulatory binder and in OnCore.

Pain will be assessed on the 10 point Visual Analogue Scale (VAS), as mild (0-3), moderate (4-7) or severe (8-10). Patients will be asked to rate the pain at the beginning, midway point (approximately 8 minutes later), and at the end of each PDT session.

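### Does the safety interval in Section 17.1 undercut the one-sided bound below 20% on which Section 16 bases the sample size?

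*Combined protocol and SAP*

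**What the plan says.** The sample-size paragraph of Section 16 fixes the type of interval first: "Safety will be evaluated using a one-sided confidence interval (as the lower bound is not of interest". It then sets the number, "At least fourteen patients will be evaluable for safety", and the precision that follows from it: "If none of the patients have an adverse primary safety outcome, the upper bound of a 95% one-sided confidence interval is < 20" percent.

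Section 17.1 defines the primary safety outcome: a grade 3 or higher or serious adverse event at least possibly related to treatment, or a related event that ends participation for good. For the analysis it says "The primary safety outcome measures will be estimated with 95% Clopper-Pearson CI", with no mention of the side.

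Three other statements bear on the number of patients. Section 2.3: "We estimate a total of 16 to 20 subjects would be enrolled in this study". Section 16, on who counts: "Evaluable subjects for safety outcome measures will be those who complete any study visits or those who discontinue the study treatments due to adverse events". Section 16, on how many are likely: "At least 15-16 evaluable subjects for each of these analyses are expected", where the analyses meant are safety and efficacy.

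**The concern.** An unqualified 95% confidence interval is normally taken as two-sided. The only other use of the Clopper-Pearson interval in the plan, for the baseline description at the start of Section 16, is most naturally read that way too. A programmer working from Section 17.1 alone could therefore report a two-sided interval. With no events at all, its upper limit would exceed 20% at 14, 15 and 16 evaluable patients.

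The bound is the only quantitative support for the trial's size, so a clean safety record might appear to miss the precision that was promised. Two further features add to the unease. Section 16 gives both 14 and 15 to 16 as numbers of evaluable patients. The assurance also covers the zero-event case alone, although Section 4.4 says of pain: "Pain is by far the most common, and limiting, adverse event associated with PDT".

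**Working it through.** **Inputs.** Zero events, 95% confidence, one-sided, n at least 14, target below 20% (Section 16); Clopper-Pearson method (Section 17.1); 15 to 16 evaluable patients expected (Section 16); 16 to 20 enrolled (Section 2.3).

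**1. The plan's own figure.** With zero events in n, the exact one-sided 95% upper bound solves (1 − p)^n = 0.05, so p = 1 − 0.05^(1/n).

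- n = 13: 1 − 0.05^(1/13) = 20.6%
- n = 14: 1 − 0.05^(1/14) = 19.3%

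The stated figure reproduces, and 14 is the smallest number that achieves it. As a cross-check, the chance of zero events when the true rate is 20% is 0.80^14 = 0.044, below 0.05, whereas 0.80^13 = 0.055 is not. The sample size was therefore derived from a one-sided exact bound, as Section 16 says.

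**2. The alternative reading.** The upper limit of a two-sided 95% interval puts 2.5% in the upper tail: p = 1 − 0.025^(1/n).

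| n evaluable | one-sided 95% | two-sided 95% |
|---|---|---|
| 14 | 19.3% | 23.2% |
| 15 | 18.1% | 21.8% |
| 16 | 17.1% | 20.6% |
| 17 | 16.2% | 19.5% |
| 18 | 15.3% | 18.5% |
| 19 | 14.6% | 17.6% |
| 20 | 13.9% | 16.8% |

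The side decides whether the limit is below 20% only at 14, 15 and 16. From 17 upward both readings meet the figure.

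**3. The two sections side by side.** Section 16 gives the side and the reason for it. Section 17.1 gives the method and the level. Clopper-Pearson is a way of building exact limits and serves for one side or two. Nothing in either section calls the safety interval two-sided. Together they specify a one-sided 95% Clopper-Pearson upper bound, which is the column that matches the plan.

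**4. The numbers of patients.** Fourteen is what the bound requires; 15 to 16 is what the investigators expect for safety and efficacy alike. Having 15 or 16 satisfies a requirement of at least 14, so the two statements do not conflict. Anyone who completes any study visit counts for safety, so the evaluable number can approach the 16 to 20 enrolled.

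**5. One event.** The one-sided bound for one event in 14 solves (1 − p)^14 + 14p(1 − p)^13 = 0.05, which gives p = 29.7%. If the true rate were 5% or 10% (assumed for illustration; the documents give no rate for this outcome), the chance of zero events in 14 would be 0.95^14 = 49% or 0.90^14 = 23%. This shows how sensitive the illustration is. It does not make the stated zero-event figure wrong.

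**The case for a change.** The best argument for a change is that Section 17.1 is where an analyst looks, and it is silent on the one feature that separates 19.3% from 23.2% at the planned minimum. If the side were truly open, it could be chosen after the data are seen. Stating it would cost a few words, and a one-event bound would tell readers more than the zero-event case alone.

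Part of this stands. Section 17.1 does not repeat the side, a hurried programmer could default to two, and at 14 to 16 patients the printed limit would then exceed 20%. The arithmetic behind the objection is correct.

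The rest is weaker. The side is not open, because Section 16 settles it for safety in advance and says why. If a two-sided interval were printed by default, the count and the denominator would still let any reader compute the planned bound. The one-event bound is a useful addition but optional; a zero-event bound is a usual way to illustrate precision in a pilot study. Pain is not itself a primary safety event. It counts only when it meets the grade, seriousness or discontinuation conditions of Section 17.1, and the documents do not say how often that happens.

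**Conclusion.** No change follows. The figure in Section 16 is right, with 19.3% at 14 patients against a stated limit of 20%. The analysis in Section 17.1 delivers that figure when the two sections are read together. What remains is a detail left unrepeated, which a competent analyst fills from Section 16.

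A default to two-sided reporting would raise the zero-event limit by 3.9 percentage points at 14 patients (23.2 − 19.3) and by 3.5 at 16 (20.6 − 17.1). It would leave the limit below 20% from 17 patients on. The consequence would be presentational. The plan does not make 20% a success criterion or a stopping boundary: Section 11.4 leaves closure for safety to the investigator's judgement, Section 17.3 plans no interim analysis, and although Section 11.6 lists stopping rules among the items reported to the monitoring board, no section sets one at 20%.

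This rests on two assumptions: that the statement in Section 16 on how safety is evaluated governs the interval in Section 17.1, as its wording indicates, and that the comparison concerns the zero-event case, the only one for which the plan makes a claim.

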17. ANALYSIS

17.1 Safety Analysis

The primary safety outcome measures will be estimated with 95% Clopper-Pearson CI: The proportion of evaluable study participants who had a grade 3 or higher AE or any serious adverse event that's determined to be at least possibly or probably related to study treatment, or any AE which is at least possibly or probably related to study treatment that causes permanent study discontinuation. AE's will be documented and kept in the study regulatory binder and in OnCore.

Pain will be assessed on the 10 point Visual Analogue Scale (VAS), as mild (0-3), moderate (4-7) or severe (8-10). Patients will be asked to rate the pain at the beginning, midway point (approximately 8 minutes later), and at the end of each PDT session.

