9.6 Early Treatment Termination

Early treatment termination visits/procedures will be conducted when the subject decides to withdraw from the study or the PI deems it necessary to end the treatment. Procedures that will be completed during the early termination visit are outlined in the Schema table Section 26.

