9.7 Off Study

Subjects will be considered off study when all planned treatment and follow-up visits have been completed, unless death or withdrawal of consent to continue participation occurs. The end of study visit will be conducted per the schema in section 26.

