15. REMOVAL OF SUBJECTS

Subjects have the right to withdraw from the study at any time and for any reason without prejudice to their future medical care by the physician or at the institution. If this occurs, the investigator, or designee, is to discuss with the subject the safe and appropriate processes for discontinuation from the investigational treatment.

The investigator or designee must document the change in status of the subject's participation in the study and as applicable, the level of follow up that is agreed to by the subject (i.e. agrees to follow up exams, adverse event review, but not to further treatment and/or procedures).

Subject withdrawal of consent for a study indicates that the subject does not wish to receive further protocol required therapies or procedures, and the subject does not wish to, or is unable to continue further study participation. Subject data only up to the time when consent is withdrawn will be included in the analysis of the study.

The study is expected to close after all patients have been treated for 3 years.

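### The primary safety outcome counts a related non-serious grade 1–2 AE only if it ends study participation, so a subject who stops PDT for one but stays in follow-up can be scored event-free

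*Combined protocol and SAP*

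**What the plan says.** Section 17.1 (Safety Analysis) defines the primary safety outcome by two routes. The first is severity or seriousness. Its wording begins "The proportion of evaluable study participants who had a grade 3 or higher AE or any serious adverse event that's determined to be at least", and the rest requires a possible or probable link to the intervention. The second is consequence, at any grade: "any AE which is at least possibly or probably related to study treatment that causes permanent study discontinuation".

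Section 16 (Statistical Considerations) defines the safety-evaluable subjects as "those who complete any study visits or those who discontinue the study treatments due to adverse events (AE"). It plans for at least 14 of them. With no primary safety event among 14, it states that the upper bound of a one-sided 95% interval is below 20%.

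Three other places bear on what leaving the study means:

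- Section 15 (Removal of Subjects) gives as an example of agreed follow-up a subject who "agrees to follow up exams, adverse event review, but not to further treatment and/or procedures". A separate paragraph deals with withdrawal of consent.
- Section 9.7 (Off Study): "Subjects will be considered off study when all planned treatment and follow-up visits have been completed, unless death or withdrawal of consent". Stopping PDT is not on that list.
- Section 9.6 (Early Treatment Termination) applies "when the subject decides to withdraw from the study or the PI deems it necessary to end the treatment", so it names the two situations as alternatives.

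No section defines study discontinuation.

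**The concern.** The denominator is written in terms of stopping treatment and the second route of the numerator in terms of leaving the study. Where the two states come apart, so do the counts.

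Take a subject who stops PDT for good after the third session because of related, non-serious grade 2 pain and agrees to later exams. There is no grade 3 event, no serious AE and, read literally, no study discontinuation. A second subject with the same AE and the same decision who also withdraws consent is an event. The AE and the tolerability failure are identical; only willingness to be followed differs.

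This matters because safety is part of the primary objective (section 3.1), eight PDT sessions are planned over three years (section 26), and section 4.4 says of the treatment: "Pain is by far the most common, and limiting, adverse event associated with PDT". Stopping PDT for a tolerability reason that is neither grade 3 nor serious is therefore foreseeable. The error has one direction: it can remove events from the composite but cannot add any.

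**Working it through.** **Step 1. Which AEs depend on the second route.** A related AE of grade 3 or higher counts by the first route. A related serious AE also counts by the first route, whatever its grade. What remains is the related, non-serious grade 1–2 AE, for which study discontinuation is the only way in.

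**Step 2. How a treatment stopper who stays in follow-up is scored.**

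| Question | Source | Answer |
|---|---|---|
| In the safety denominator? | Section 16 | Yes: has completed a visit, and also stopped treatment for an AE |
| Off study? | Section 9.7 | No: visits not complete, no death, no withdrawal of consent |
| Is this status foreseen? | Section 15 | Yes: exams and AE review without further treatment |
| Event by the first route? | Section 17.1 | No: grade 1–2, not serious |
| Event by the second route? | Section 17.1 | Not on the literal wording |

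The subject is thus counted as event-free rather than excluded.

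**Step 3. Reproduce the plan's figure.** Inputs from section 16: n = 14, 0 events, one-sided 95%. For 0 events the exact (Clopper-Pearson) upper bound is 1 − 0.05^(1/n).

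- n = 14: 1 − 0.05^(1/14) = 19.26%, below 20% as stated.
- n = 13: 1 − 0.05^(1/13) = 20.58%, so 14 is the smallest size that meets the statement.

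The plan's figure is right.

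**Step 4. Illustrate one reclassified subject.** For x events the upper bound is the 95th percentile of a Beta(x + 1, n − x) distribution.

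| n | 0 events | 1 event |
|---|---|---|
| 14 | 19.26% | 29.67% |
| 15 | 18.10% | 27.94% |
| 16 | 17.07% | 26.40% |
| 20 | 13.91% | 21.61% |

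At n = 14 the point estimate moves from 0% to 1/14 = 7.1%, and the bound rises by 29.67 − 19.26 = 10.4 percentage points. Section 17.1 does not say whether its 95% interval is one- or two-sided. If two-sided, the upper limits are 23.16% for 0/14 and 33.87% for 1/14, a similar shift of 10.7 points.

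**Step 5. How likely is at least one such subject?** The documents give no rate. As an assumption only, let p be the chance that a subject permanently stops PDT for a related non-serious grade 1–2 AE and stays in follow-up. Then the chance of at least one among 14 is 1 − (1 − p)^14: 51% at p = 5%, 77% at p = 10%, 96% at p = 20%. Nothing in the protocol says which of these, if any, applies.

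**The case against.** The strongest reply is that the two states hardly come apart in this trial. Section 9.5 says there are no follow-up visits other than the end-of-study visit. Section 9.6 uses a single early-termination visit for both triggers. The schedule in section 26 has no off-treatment visits and places the end-of-study visit three months after the last treatment. The section 15 wording comes directly after a sentence on the right to withdraw from the study, so a subject who declines further PDT could be seen as one kind of withdrawing subject and would then already count. Section 16 suggests that the sponsor had treatment discontinuation in mind throughout.

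Much of this stands. It limits how many subjects could be affected and makes loose wording a plausible explanation. It does not close the gap. Section 15 keeps withdrawal of consent apart from declining treatment, section 9.7 does not treat stopping PDT as going off study, and section 9.6 lets the investigator end treatment for a subject who has not withdrawn at all. Two analysts could score the same subject differently.

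It is also fair to say that such stops would not be hidden. The AE form in section 11.5 records grade, relationship and action taken, the DSMB receives AE narratives every six months, and pain is scored three times per session. The gap is in the composite outcome, not in data collection.

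**Conclusion.** The point holds as a mismatch of terms in the primary safety outcome that should be corrected before analysis. On the literal text, a permanent PDT stop for a related non-serious grade 1–2 AE is not an event if the subject remains in follow-up, and the resulting error can only favour the treatment.

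Three stronger readings may tempt a reader, and the documents do not support them:

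- *One uncounted subject overturns the trial's safety conclusion.* The 20% figure is a conditional precision statement for zero events, with no success or stopping threshold attached. A single event by any route would take the bound above 20%, even at n = 20, which reflects the small sample rather than this wording.
- *Better retention after stopping PDT will make the treatment look markedly safer.* The schedule offers almost no off-treatment follow-up, so this can operate only through whatever follow-up is agreed subject by subject.
- *Every grade 1–2 AE depends on this component.* Related serious AEs count at any grade.

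The size is therefore conditional: if one such subject occurs, the upper bound is 29.7% instead of 19.3% at n = 14 (26.4% instead of 17.1% at n = 16). How often it will occur cannot be derived from the documents.

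**What to change.** In section 17.1, replace the requirement of permanent study discontinuation in the second route with: *causes permanent discontinuation of study treatment (PDT), whether or not the subject remains in follow-up*. This brings the numerator into line with the term that section 16 uses for the denominator and removes the dependence on how sections 9.7 and 15 are read.

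No new data are needed: the action-taken field on the AE form in section 11.5 already has discontinued as an option. The sample size statement in section 16 does not change. The cost is one phrase in an amendment and a reported safety proportion that may be slightly less favourable. If treatment discontinuation was what the sponsor meant, the change only records that intent.

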17.2 Efficacy Analysis

Number of AK/NMSC will be counted for each site using the photographs of the treatment and the control areas. AKs will be graded by thickness I-III: I = mild, slightly palpable, II = moderate, easily felt, III= severe, very thick. NMSC, including basal cell carcinoma, Bowen's disease and squamous cell carcinoma, will be diagnosis and confirmed histologically by biopsy.

Photo damage in the treatment and control fields will be assessed by the sun damage scale as: absent, mild, moderate, and severe. The scale includes 4 points: fine wrinkling, coarse wrinkling, abnormal pigmentation and global (0-10). Ratings for epidermal dysplasia will be obtained by immunohistochemistry of p53 staining of skin biopsies in the treatment areas at baseline and after the last treatment.

Time to occurrence of AK/NMSC will be calculated from the first visit to the development of an AK or NMSC in the treatment areas and in the control areas.

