2. STUDY DESIGN

2.1 Phase

This is a pilot, phase 2, prospective, comparative study. Each subject will undergo split-side face and dorsal forearm/hand PDT treatment at: Day 1 (initial treatment), Day 30 (1 month after initial treatment), Day 180 (6 months after initial treatment), 1 year after initial treatment, and every 6 months thereafter for 2 additional years.

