7. STUDY PLAN

7.1 Intervention Regimen

Levulan® Kerastick® for Topical Solution will be applied to a designated area for 1 hour without occlusion prior to illumination with blue light using the standard FDA approved treatment time for the BLU-U device of 16 minutes 40 seconds. Each subject will be randomized to undergo treatment to one side face and one dorsal forearm/hand treatment, while the other side will serve as untreated control. Treatments will be conducted at the beginning of study Day 1 (Initial Treatment), Day 30 after the initial treatment (\pm 3 days), Day 180 after initial treatment (\pm 30 days), 1 year after the initial treatment (\pm 30 days), and every 6 months (\pm 30 days) thereafter for 2 additional years.

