8. REQUIREMENTS FOR TREATMENT

8.1 Standard intervention

Levulan® Kerastick® for Topical Solution will be applied to the designated area for 1 hour without occlusion prior to illumination with blue light using the BLU-U for 16 minutes 40 seconds (FDA approved treatment time). Each subject will undergo treatment on one side face and dorsal forearm and hand treatment, while the other side will serve as an untreated control. Treatments will be conducted at the beginning of study Day 1 (Initial Treatment), Day 30 after the initial treatment (\pm 3 days), Day 180 after initial treatment (\pm 30 days), 1 year after the initial treatment (\pm 30 days), and every 6 months (\pm 30 days) thereafter for 2 additional years. Focal treatment procedures such as liquid nitrogen, excisional surgery, electrodesiccation and curettage or Mohs surgery,

for precancerous or skin cancers in intervention sites or control sites, will be performed as necessary.

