9.2 Registration/Randomization

All regulatory requirements must be in place prior to subject registrations.

UACC subject identification numbers will begin with 100 and will be assigned sequentially.

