10.2 Processing

All skin biopsy specimens will be sent and processed at the University of Arizona Cancer Center in Tucson, in [name] laboratory..Karyometry analysis will be done at [name] laboratory for all specimens. Karyometric measures of nuclear abnormalities scores will be recorded for statistical analysis.

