Appendix 3. Digital Photography

Digital photographs will be taken using a Nikon COOLPIX 4300 digital camera (Nikon, Tokyo, Japan) with standardized methods to ensure consistency. Standardized lighting will be available using overhead lighting and no separate skin illumination. The Anytime Flash setting will be used with maximum aperture (preset between 2.8 and 7.6), and all photographs will be taken on a uniform blue background. Additional settings include image size, 2272 × 1704; image quality, fine; focus, macro close-up automatic single mode; and sensitivity, 100 ISO. The focal length of the COOLPIX lens system is 8 to 24 mm.

Source: Arch Dermatol. 2011 Jan; 147(1): 31-36. PMID: 21242389.

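### The primary AK/NMSC count is read from photographs with no stated step to hide the treated side, which leaves the AK part of the count open to reader bias

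*Combined protocol and SAP*

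**What the plan says.** Section 16 defines the primary outcome: "Primary efficacy outcome measure will be the difference in the total number of AK/NMSC in the treatment areas compared to the control areas". All unique lesions over three years are summed per area, and the paired difference goes to a Wilcoxon signed-rank test. Section 17.2 gives the source of the count: "Number of AK/NMSC will be counted for each site using the photographs of the treatment and the control areas". It requires histological confirmation for NMSC, including Bowen's disease. AK is graded by thickness, in terms of how it feels, and no histology is required.

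Section 7.1 randomises each subject to treatment of one side of the face and one forearm/hand, "while the other side will serve as untreated control". Section 8.1 repeats this: "while the other side will serve as an untreated control". Neither mentions vehicle or sham light.

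The places where masking might be described do not describe it:
- Section 2.1 gives the design as "This is a pilot, phase 2, prospective, comparative study".
- Section 9.2, on registration and randomisation, covers regulatory readiness and numbering: "UACC subject identification numbers will begin with 100 and will be assigned sequentially".
- Appendix 3 has photographs taken "with standardized methods to ensure consistency", which covers camera, lighting and background.
- Section 10.2 sends biopsies to the laboratory and says "Karyometric measures of nuclear abnormalities scores will be recorded for statistical analysis", with no coding step.

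**The concern.** Randomising the side balances the skin before treatment. It does nothing about a reader who later judges the two sides differently. With an untreated control, the subject and the treating staff know which side had photodynamic therapy (PDT), and nothing in the plan keeps this from the person who counts.

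Early AK is a borderline call. Section 6.1 admits only subjects with no earlier NMSC in the treatment fields and no AK or Bowen's disease there in the preceding three months. New, thin AKs could therefore plausibly make up much of the count. The same calls also determine time to first AK/NMSC.

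At stake is what a positive primary result would mean: a signed-rank test on paired counts cannot tell a reading difference from a preventive effect.

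**Working it through.** **The plan's own figure.** The only sample-size figure is for safety (section 16): with no events in 14 subjects, the one-sided 95% upper bound is below 20%. It reproduces: 1 − 0.05^(1/14) = 19.3%. It has no bearing on efficacy. The plan gives no lesion rate, effect size or power for the primary count, so the check has to be a simulation on assumed inputs.

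**Inputs from the documents**
- Evaluable subjects for efficacy: 15-16 (section 16); 16 used.
- Test: Wilcoxon signed-rank on paired counts (section 16).
- One anchor for the lesion rate: section 4.4 cites a trial with AK in 63% of patients in untreated skin at 3 years.

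**Assumptions**
- Two-sided 5% level (the plan states none for efficacy).
- Subject rate λ ~ Gamma with shape 1 and mean μ, shared by both sides.
- Control count ~ Poisson(λ); treated count ~ Poisson(rλ). There is no true effect, so r < 1 is under-counting alone.
- μ = 1.7 or 4. With shape 1, P(at least one lesion) = μ/(1+μ). This gives 1.7/2.7 = 63%, matching the anchor, and 4/5 = 80% for a higher-burden case.

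**Result.** False-positive rate, n = 16, exact signed-rank test, 4,000 runs per setting (ranges are over repeat runs):

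| Mean lesions per side | Equal counting | 10% fewer on treated side | 25% fewer | 40% fewer |
|---|---|---|---|---|
| 1.7 | about 4% | 4.4-4.8% | 10-11% | 23-26% |
| 4 | 3.8-4.5% | 6.8-7.2% | 24-25% | 54-55% |

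In lesions, 25% under-counting is an expected 16 × 1.7 × 0.25 = 6.8 across the whole trial at mean 1.7, and 16 × 4 × 0.25 = 16 at mean 4.

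**Sensitivity.** The same model with the normal approximation and other means, n = 16:

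| Mean lesions per side | Equal | 10% fewer | 20% fewer | 30% fewer |
|---|---|---|---|---|
| 2 | 4.6% | 5.5% | 11.6% | 19.5% |
| 5 | 4.2% | 8.1% | 21.9% | 42.4% |
| 10 | 5.3% | 12.0% | 34.6% | 67.8% |

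At n = 15 and mean 5 the rates are 4.9% (equal), 19.3% (20% fewer) and 36.9% (30% fewer). Once under-counting reaches 20%, nearly all false positives favour the treated side.

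**Limit of the model.** It thins all treated-side lesions, while histology protects NMSC against false calls. If AKs were 80% of the count (an assumption), a 25% overall shortfall would require missing 0.25/0.80 = 31% of treated-side AKs.

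**The case against.** The case against has several parts, and some of it stands.

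- **Silence is not an unmasked procedure.** A reader might infer that the photographs carry treatment and control labels, or that the reader is known to be aware of the side. Section 17.2 says only which areas are photographed; no label, reader or reading order is described. The front matter was not available, so a masking label there cannot be excluded. What stands is that no procedure in the body hides the side.
- **The count is not wholly unprotected.** Histology guards against false NMSC calls, though not against unequal choice of lesions to biopsy. The exposed part is AK.
- **The size is assumed.** The under-count fractions and mean 4 have no source in the documents. The 63% comes from patients with clinically normal skin, whereas section 6.1 requires moderate to severe sun damage. At 10% under-counting the inflation is small or absent. All of this stands.
- **Masking could damage the endpoint.** Scrambling subject, side and visit would stop the reader telling a persistent AK from a new one, and section 16 counts unique lesions. This is right, and the fix below keeps visits linked.
- **Masking may be incomplete.** The reader is not named. If that person also treats the subjects, 16-20 people seen at eight treatment visits may be recognised. Thickness grading and focal treatment take place in person and stay outside any photograph coding. This limits the benefit without removing it.
- **The laboratory case is weaker.** Biopsies are read in Tucson and the clinic is in Phoenix, so staff awareness in the clinic does not extend to the laboratory by itself. Section 17.2 takes p53 from treatment areas only, so there is no side to hide there. Neither measure is primary.

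**Conclusion.** The concern holds in a limited form. As written, the plan compares a treated with an untreated side on a photograph count whose AK part is a judgement without histological check, and it states no step that hides the side.

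Under the assumptions above (n = 16, mean 1.7 to 4 lesions per side, gamma frailty with shape 1, two-sided 5%), the false-positive rate is about 4-5% with equal counting, about 4-7% with 10% fewer treated-side lesions counted, and about 10-25% with 25% fewer. Higher lesion burdens make it more sensitive.

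A reader might infer from these figures that the trial will be biased, or by a given amount. The documents do not support that: they give no reading error, and the simulation shows only what unequal counting would do if it occurred. The point is worth acting on even in a pilot, because the gap affects the primary comparison and closing it needs no new visit or procedure.

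**What to change.** In section 17.2, state that:
1. The study coordinator gives each subject-side photograph series one random code, crops the images, and randomly mirror-flips whole series so that left and right are hidden.
2. Visits stay linked and in order within a series, so that unique lesions and the time of the first one can be followed.
3. The planned reader counts AKs series by series in random order, and the side key is released only after the counts are locked.
4. In-person AK thickness grades and histologically confirmed NMSC are recorded separately and merged with the masked counts after lock.

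In section 10.2, state that slides are sent under accession codes that hide side and visit for karyometry, and visit for p53.

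The cost is some coordinator time. The photographs and biopsies are already scheduled in section 26, so no visit, procedure or reader need be added. Masking may be imperfect where skin reaction, scars or the reader's familiarity with a subject reveal the side.
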